Aim 3: Determine the influence of a menthol flavor ban on tobacco purchasing behavior in the context of a reduced nicotine standard using an ETM. At Visit 5, participants will complete two ETMs in the laboratory to model the impact of menthol flavoring and nicotine content on cigarette purchasing in the context of all available tobacco products currently on the market. ETM 1 will evaluate willingness to purchase and smoke non-menthol VLNCs at increasing prices under the scenarios where a

nicotine reduction policy is in effect and menthol is banned in combustible cigarettes. ETM 2 will evaluate willingness to purchase and smoke menthol vs non-menthol VLNCs at increasing prices under the scenario where a nicotine reduction policy is in effect but menthol in combustible cigarettes is available. In both ETMs, all ATPs will be available in different flavors, including menthol, to simulate the real-world marketplace. Hypothesis: In ETM 1, YAs will be more likely to choose an ATP than purchase any cigarettes. In ETM 2, YAs will be more likely to purchase menthol VLNCs or ATPs than purchase non-menthol VLNCs or no tobacco products.

Exploratory Aim: Determine the influence of a menthol flavor ban on tobacco purchase behavior when menthol is banned in all combustible tobacco products (cigarettes, cigars), but is available in non-combustible products (e.g., e-cigarettes).

The proposed research design is unlike existing research, as it combines rigorous, controlled laboratory paradigms of smoking response with “real-world” measurements of the same to determine the relative impact of menthol characteristics and nicotine on cigarette smoking in YAs, a vulnerable group of tobacco users, and adults aged 26-34, who also have high rates of menthol cigarette use. Beyond informing policy, this proposal will validate a new set of measures to be used in future studies to evaluate the potential impact of tobacco policies (e.g., a ban on all flavors) on YA cigarette and alternative tobacco use behavior.

B. Background and Significance

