At the end of V2, participants will receive the first set of assigned research cigarettes and will be asked to smoke those cigarettes in their home environment for 7 days; starting on the day after V2. The ordering of flavor of the research VLNCs to be smoked (menthol and non-menthol) will be counterbalanced and assigned prior to Visit 2 (Individuals who complete the session remotely will be scheduled for a pick-up date to get the VLNCs1). During each 7-day period of exposure, participants will be instructed to switch their usual brand cigarette for the assigned research cigarette and will provide daily data on smoking quantity, craving, withdrawal, subjective response, and alternative tobacco product use via twice daily EMA surveys. We will allow for other tobacco product use without specific instruction to align with the real-world scenario, as these products will exist on the market even if a menthol ban and/or a reduced nicotine standard are enacted. Given the high prevalence of dual and poly-tobacco use in this age group, we will examine change in alternative tobacco product use between conditions as a secondary outcome in exploratory analyses, per Co-I [name]'s and [name]'s previous work. Participants will have a 7-day period wash-out period of return to smoking as usual (own brand of cigarette) between the experimental conditions.

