C.6. Laboratory Visit 5 (V5) and ETM Procedure. Participants will complete the ATSQ, mFTQ, MNWS, and QSU after which two separate ETM³⁻⁶ tasks (counterbalanced) will be administered at the conclusion of the laboratory and take home trials (V5) to >12 hour abstinent participants. In the tasks, participants will be shown an online virtual ‘marketplace’ of cigarettes and all combustible and non-combustible tobacco products that are available on the market. Participants will be instructed to complete the task as if they were purchasing the products from a retailer, and told to make purchases of cigarettes and/or alternative tobacco products that they would take home and use for the week. The price of cigarettes will increase over eight trials (\$0.12, \$0.25, \$0.50, \$1.00, \$2.00, \$4.00, \$8.00, and \$16.00 per cigarette). The prices of alternative products available on the market will remain fixed, and will reflect the average cost of these products in Oklahoma. The first iteration of the task (ETM 1) will assess participant’s willingness to purchase non-menthol VLNCs at increasing prices, where no other types of cigarettes will be available (e.g., menthol NNCs; menthol VLNCs); this will model a scenario where a nicotine reduction policy is in effect and menthol in combustible cigarettes is banned. Findings from ETM 1 will inform FDA whether the presence of menthol-containing tobacco products, beyond cigarettes, leads to significant changes in combustible and non-combustible product use. The second iteration of the task (ETM 2) will assess participant’s willingness to purchase menthol VLNCs at increasing prices, where non-menthol VLNCs are available but no other cigarette types (e.g., NNCs) are available; this will model a nicotine reduction policy without a menthol ban. The prices for non-menthol VLNCs in ETM 1 and menthol VLNCs in ETM 2 will be presented at increasing prices. All alternative tobacco products presented in the ETMs will be available in different flavors, including menthol, to simulate the real-world marketplace.

Participants will receive account balances approximately equal to the money they spend on tobacco in one week. They will be instructed that they can ‘save’ unspent money, and purchase as many or few tobacco products as their account balance allows, including no tobacco products at all. Results of the ETM will not be actualized – meaning the ETM will be hypothetical and they will not receive

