Patterns of missing data, compliance, distributional properties of variables, and correlations among all measures will be assessed. We will control for potential variables related to missing data and utilize multiple imputation methods (expectation maximization algorithm).¹⁶⁰⁻¹⁶³ Analysis will use linear mixed modeling with random subjects effects^{164,165} to assess the main effect of cigarette type on the primary and secondary outcomes of interest. Models will use a contrast to compare differences between menthol VLNC and non-menthol VLNC at the day-level on predictions of the outcome of interest and that outcome of interest at time t (e.g., morning) predicting behavior (number of cigarettes, any smoking, craving, withdrawal) occurring at a subsequent time point (controlling for cigarette consumption from the previous report). Comparison of usual brand and the menthol VLNC ratings will also be made to determine the perceived similarity of the VLNC to one's own brand. A sub-group of respondents may have fixed (unchanging) ratings of subjective response, craving, cigarettes per day, or withdrawal over the course of 7 days, although this is unlikely given the team's previous research. We will examine baseline and daily factors that set "no changers" apart from those whose show fluctuations in these factors, and examine these as potential covariates in models. Within-person slopes capturing associations between cigarette type and the EMA outcome of interest will be saved in regression models and used to predict the ETM responses.

4. ETM Analyses (Aim 3)

Primary Outcomes: (a) consumption of alternative tobacco products (milligrams of nicotine for alternative tobacco sources) as a function of cigarette type available. Typically, as cigarette price increases, consumption of other tobacco products increases.¹⁴ Secondary Outcomes: (a) breakpoint: the first price at which consumption of the available cigarette is zero; (b) intensity of demand: consumption at the lowest price); (c) elasticity of demand: sensitivity of cigarette consumption to increases in cost, (d) Omax: maximum expenditure for cigarette type available; and (e) Pmax: price at which expenditure is maximized.

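### The ETM 1 hypothesis names no price and no ETM 2 comparator, so it can be met with no menthol-ban effect, and section J.4 specifies no ETM 1 versus ETM 2 contrast

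*Combined protocol and SAP*

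**What the plan says.** **Aim 3 (A. Specific Aims).** The aim is the influence of a menthol ban on purchasing under a reduced nicotine standard. ETM 1 offers non-menthol VLNCs only; ETM 2 offers menthol and non-menthol VLNCs. The ETM 1 hypothesis is "In ETM 1, YAs will be more likely to choose an ATP than purchase any cigarettes". The ETM 2 hypothesis puts menthol VLNCs or ATPs ahead of non-menthol VLNCs or no purchase. Neither names a price, a unit of analysis or the other task.

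**Procedure (C.6).** "The price of cigarettes will increase over eight trials": $0.12, $0.25, $0.50, $1, $2, $4, $8 and $16 per cigarette. For ATPs, "The prices of alternative products available on the market will remain fixed, and will reflect the average cost of these products in Oklahoma". The budget is about one week's tobacco spending. On which cigarette is escalated, "The prices for non-menthol VLNCs in ETM 1 and menthol VLNCs in ETM 2 will be presented at increasing prices".

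**Analysis (J.4).** The primary outcome is ATP consumption in milligrams of nicotine, by cigarette type available. The plan then remarks: "Typically, as cigarette price increases, consumption of other tobacco products increases". The models are hierarchical regressions of ETM outcomes on laboratory or EMA appeal, fitted separately for each cigarette type. Other tobacco use is a Step 1 covariate.

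**Existing ATP use.** The V2 section refers to it: "Given the high prevalence of dual and poly-tobacco use in this age group". Among ATP-type products, section F excludes only current users of nicotine replacement therapy.

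**Menthol in other products (C.6).** "Findings from ETM 1 will inform FDA whether the presence of menthol-containing tobacco products, beyond cigarettes, leads to significant changes". Aim 3 and C.6 both keep menthol ATPs available in ETM 1 and in ETM 2.

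**The concern.** A claim about a ban needs a comparison between a marketplace with the ban and one without it. The ETM 1 hypothesis instead orders two kinds of purchase within the banned marketplace. Three influences other than the ban push that ordering towards ATPs:

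- **Price.** Only cigarettes become dearer, and J.4 itself expects ATP use to rise with cigarette price.
- **Existing use.** Participants who already use ATPs may buy them whichever cigarettes are on offer.
- **Nicotine.** ETM 1 imposes the low-nicotine standard together with the ban. The Aim 2 hypothesis expects more ATP use than with usual brand in both VLNC conditions, so the plan anticipates a shift from low nicotine alone.

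The ETM 2 hypothesis does not repair this, because ATPs are on its favoured side too. Participants who mostly buy ATPs, identically in both tasks, would satisfy both hypotheses with a ban effect of exactly zero. C.6 presents ETM 1 as informing FDA, so a confirmed hypothesis could be taken as evidence on a ban that it does not contain.

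**Working it through.** The plan gives no figure for this hypothesis to reproduce: no price, test, effect size or rate.

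**1. Price ladder (C.6).** The range is 16 / 0.12 = 133-fold. Per 20 cigarettes (an assumed pack size), price × 20 gives $2.40, $5, $10, $20, $40, $80, $160 and $320; six of the eight are $10 or more.

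**2. Budget.** The largest whole number affordable is balance / price, rounded down. For assumed weekly balances of $10, $30 and $100 it is 83, 250 and 833 cigarettes at $0.12, but 0, 1 and 6 at $16. The upper trials can suppress cigarette purchase through price and budget alone.

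**3. Can the hypothesis be met with no ban effect?** Illustration; every input is an assumption except the eight prices and n = 100 (the analytic sample in J.1).

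- Cigarette purchase probability at price p is 0.95 / [1 + (p/h)^1.5]. The price h at which it halves has a median of $0.50, $1 or $2 and varies between people (log-scale SD 0.7).
- ATP purchase probability is 0.80 for existing users and 0.10 for others, at every price. With a share u of users, the mean is 0.10 + 0.70u: 0.31, 0.45 and 0.59 for u = 30%, 50% and 70%.
- Probabilities are identical in ETM 1 and ETM 2, so the ban effect is zero.
- Test: each person's ATP rate minus cigarette rate over eight trials, one-sample t above 1.96, 2,000 runs.

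Each cell gives the mean difference (ATP minus cigarettes), then the share of runs confirming the ETM 1 hypothesis.

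| Median h | Mean cigarette rate | u = 30% | u = 50% | u = 70% |
|---|---|---|---|---|
| $0.50 | 0.31 | 0.00; 2% | 0.14; 93% | 0.28; 100% |
| $1.00 | 0.42 | −0.11; 0% | 0.03; 12% | 0.17; 99% |
| $2.00 | 0.53 | −0.22; 0% | −0.08; 0% | 0.06; 34% |

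The differences can be checked by hand: for h = $0.50 and u = 50%, 0.45 − 0.31 = 0.14. The mean cigarette rate is the average of the purchase formula over the eight prices at the median h.

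At the lowest price alone, the hypothesis was confirmed in 0% of runs in all nine scenarios. The cigarette rate there is 0.85 to 0.94 at the median h, against an ATP rate of at most 0.59.

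**4. The alternative test.** In the same runs, the within-person ETM 1 minus ETM 2 difference in the same measure rejected (two-sided, 1.96) in 4.7% to 6.3% of runs, near the nominal 5%. Both tasks impose the nicotine standard, so this contrast also removes the nicotine effect.

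**5. Is that test in the plan?** The J.4 primary outcome varies by cigarette type available, which implies a comparison of marketplaces. The J.4 models contain no ETM 1 versus ETM 2 term and no price term. Adjustment for other tobacco use belongs to the prediction models, which do not test this hypothesis.

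**6. Menthol ATPs.** Menthol in ATPs is the same in ETM 1 and ETM 2, so neither task, nor their difference, shows what its presence does. ETM 3, at the 30-day follow-up, is the only task that changes it.

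**The case against.** The strongest reply is that the primary outcome already points to the right comparison. It is defined by cigarette type available, and the focal VLNC rises in price in both tasks, so an ETM 1 versus ETM 2 comparison could largely match on price. This stands as partial mitigation: the data will exist and the outcome wording invites the contrast. But J.4 never specifies it, and the hypothesis does not use it. C.6 also leaves open whether non-menthol VLNCs rise in price in ETM 2. If they do not, cigarettes as a group are not priced alike in the two tasks.

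A second reply is that rising prices are how such a task works. That is right. The ladder is needed for breakpoint, elasticity, Omax and Pmax; the objection is only to a choice hypothesis with no price attached.

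Three stronger readings are tempting, and the documents do not support them:

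- A reader might infer that price and dual use will produce ATPs ahead of cigarettes under any test. The table shows otherwise: five of nine scenarios confirm in 12% of runs or fewer, a sixth in 34%, and none at the lowest price. Pooling the eight trials is itself an assumption.
- A reader might infer that most trials are above market price. The documents give no market cigarette price, ATP price or pack size.
- A reader might infer that the sponsor will report the ETM 1 ordering as a ban effect. No section says so.

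**Conclusion.** The concern holds in a limited form. As worded, the ETM 1 hypothesis can be confirmed with no menthol-ban effect, because it has no price and no comparator and ETM 1 combines the ban with the nicotine standard. Whether it would be is unknown: 0% to 100% over the assumed range, depending on price sensitivity and the share of existing ATP users, neither of which the documents give. Those percentages are illustrations of dependence, not forecasts. The simulation holds ATP purchase constant over price and so leaves out the substitution that J.4 expects.

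The gap is in the hypothesis and the analysis, not in the design. Both marketplaces are administered to the same people, so the needed contrast can be formed from planned data, subject to how non-menthol VLNCs are priced in ETM 2. The plan should be changed, but Aim 3 is not lost. The documents give no effect size or SD for any ETM outcome, so what this contrast could detect with n = 100 cannot be calculated. The C.6 sentence on menthol products beyond cigarettes is a smaller, separate mismatch.

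**What to change.** 1. **Aim 3.** Restate the hypothesis as a within-person difference between ETM 1 and ETM 2 in ATP purchase, at a stated reference price or price set. A reference price inside ETM 1 alone would not be enough, because it leaves the ban and the nicotine standard confounded.
2. **J.4.** Add that contrast at matched cigarette prices, for ATP nicotine in milligrams and for any ATP versus any cigarette. Include baseline ATP use from the V2 Timeline Follow-Back as a covariate. Do not remove ATP classes already used at baseline from the count of switching: increased buying by existing users is real substitution, and the 7-day window would misclassify intermittent users.
3. **C.6.** State whether the non-menthol VLNC price also rises in ETM 2. If it is held fixed, say at which trials the two marketplaces are price-matched and limit the contrast to those.
4. **Price ladder.** Keep all eight prices for the demand curves.
5. **C.6, menthol beyond cigarettes.** Attach that sentence to the ETM 1 versus ETM 3 comparison, noting that ETM 3 comes 30 days later.

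Cost: wording in Aim 3 and C.6 and one added analysis in J.4, with no new assessments. The downside is that the hypothesis becomes harder to confirm.

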Drawing on the Dual-Reinforcement Model of Smoking as the scientific premise to understand the effects of a menthol ban on a reduced nicotine standard,³³ this study uses a multi-method design to measure appeal/reinforcement and abuse liability of menthol vs non-menthol VLNCs that addresses prior studies' methodological limitations and will inform FDA regulation of tobacco products. We will recruit 172 menthol smoking YAs and adults aged 26-34 who started smoking regularly ("somedays/everyday") < 6-months ago, and assess appeal/reinforcement to smoking SPECTRUM menthol and non-menthol VLNCs (0.4mg/g) and the impact of smoking appeal/reinforcement on tobacco purchasing behavior using a validated Experimental Tobacco Marketplace (ETM) task.¹³⁻¹⁶ The ETM will allow us to anticipate how smokers will respond to new product standards and policies after experimenting with these products: one in which nicotine in cigarettes is reduced; and one in which nicotine in cigarettes is reduced and menthol is banned. Appeal/reinforcement will be assessed via complementary measurement paradigms: one in the laboratory using puff topography measures and the other in the natural environment, using ecological momentary assessment (EMA).

An additional 88 participants will be added to the study recruitment analytic sample size goal of 172 YA ages 18-26 and adults aged 26-34 years to accommodate for participants found ineligible at baseline. Therefore, the total enrollment (as defined by The University of Oklahoma Health Sciences Center Institutional Review Board) goal will be a maximum of 260 YA ages 18-26 and adults aged 26-34 years "someday/everyday" menthol smokers.

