This proposal will answer important policy relevant questions about the ways in which menthol smokers could be influenced by FDAs regulatory actions to bring VLNCs to the market AND ban menthol in combustible cigarettes. If smoking menthol VLNCs translates into greater appeal and cigarette consumption relative to smoking non-menthol VLNCs in YAs and adults aged 26-34 who are new to smoking, this provides further evidence that menthol in cigarettes, even with low levels of nicotine, could be a public health hazard. This would support FDA’s authority to take additional regulatory actions toward the distribution, manufacture, or marketing of menthol to improve public health. These actions

could include extending the flavored cigarette ban to cigarettes (distribution), restricting menthol cigarette sales to adult-only venues (distribution), limiting the amount of menthol allowed in cigarettes (manufacture), and reducing menthol appeal through public health campaigns or warnings (marketing).

Conceptual Framework and Scientific Premise.

The scientific premise for this study relies on Dual-Reinforcement Model of Smoking.³⁴ According to this model, nicotine has two key effects on reinforced behavior: (1) nicotine acts as a primary (unconditioned reinforcer) that can support the establishment of associated stimuli as conditioned reinforcers, and (2) nicotine enhances the effectiveness and reward value of non-nicotine reinforcers directly, through non-associative mechanisms. The latter is exemplified by studies in which nicotine, administered in a manner unrelated to any cues or behavior, increases operant responding for both unconditioned and conditioned reinforcers.³⁵⁻³⁸ As applied to the current study, this model proposes that menthol smoking is a function of menthol acting as a conditioned reinforcer, as a consequence of its association with nicotine (and possibly other primary reinforcers, e.g., sweeteners) and because nicotine may further enhance the conditioned reinforcing effects of menthol.

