Biospecimens will be collected prospectively. Biospecimens to be collected will be expired breath analysis of carbon monoxide level to determine smoking recency. This is a non-invasive procedure conducted by blowing air through a Smokerlyzer tube. We are also collecting pregnancy tests prior to each smoking visit, to determine study eligibility. Pregnancy tests will be discarded and not kept. All biospecimen data collection will be de-identified and associated only with a unique ID number. The participant's biospecimens (even if identifiers are removed) will not be used for commercial profit. The research will not include whole genome sequencing (i.e., sequencing of a human germline or somatic specimen with the intent to generate the genome or exome sequence of that specimen).

E. Banking/Repository/Database

All data collected during the study will be retained for future use in tobacco and nicotine research. Data will be stored electronically on a secure password server that can only be accessed by approved study personnel. Only data, no samples, will be stored.

F. Inclusion / Exclusion Criteria

1. Inclusion criteria for participants will include:
 - a. Ages 18 to 34;
 - b. Smoke cigarettes “somedays” or “everyday” for at least the past 3-months;
 - c. A strong preference for menthol cigarettes (i.e., smoke menthol $\geq 80\%$ of the time)¹²⁴;
 - d. Ability to read English at an 8th grade level or higher; and
 - e. No immediate plans to quit smoking.
2. Exclusion criteria for participants will include:
 - a. Current use of nicotine replacement therapy (NRT);
 - b. Pregnant, planning to become pregnant, or currently breastfeeding (verified by pregnancy test at each study visit/virtual smoking session);
 - c. Past or current self-reported clinically significant heart disease or hypertension, or other smoking-related disease (by history) that preclude successful study completion;
 - d. Serious psychiatric disorder, as evidenced by any of the following
 - i. Ever schizophrenia, schizoaffective disorder, or bipolar disorder;
 - ii. Psychiatric hospitalization in the past year;

IRB NUMBER: 11865
IRB APPROVAL DATE: 11/16/2023

- iii. Suicidal ideation in the past month or any past year suicide attempt
 - 1. Suicidal ideation determined by the MINI suicide subscale (Questions 1-3)
 - 2. Any suicide attempts in the past 10 years (MINI suicide subscales Questions 5 and 6)
- iv. Suicidal intent and plan (MINI suicide subscale Question 4)

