- v. PHQ-9 score of 15 or higher, indicating moderately severe depression, if participant also indicates suicidal intent or worsening depression in the past 3-months. Scores of 20 or higher, indicating severe depression will be excluded.
- vi. Worsening symptoms of depression or anxiety in the past 3-months (as determined by Medical History Questionnaire).

If a participant indicates that he/she currently has suicidal ideation during the baseline or any future session, the Suicide Risk SOP protocol will be followed in which a Licensed Clinician will be contacted immediately (if that clinician is not already conducting the assessment). Participants will speak with the clinician in person, over the phone (or via Zoom) and the clinician will determine the appropriate action to take to keep the participant safe. See Suicide Risk SOP for more detail. This SOP follows the same protocol outlined in the OUHSC Tobacco Treatment Research Program (TTRP) and has been approved by the OUHSC IRB.

- e. Inability to abstain from nicotine/tobacco products and caffeine prior to study visits;
- f. Strong preference for non-menthol cigarettes (smoke non-menthol > 80% of the time)¹²⁴

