All participants will need to provide an ID that indicates their age in order to participate. If a participant is enrolled remotely, participants will be asked to email a picture of their ID to the study email, or show an image of their ID to study personnel via a Zoom session so it can be verified prior to being enrolled in the study. Eligible participants will not have immediate plans to quit smoking, and will be “someday” or “everyday” smokers for at least the last 3 months, thus the laboratory and take home smoking will confer no additional risks beyond their usual smoking. We will exclude individuals who report immediate plans to quit smoking or who are currently trying to quit smoking at the screener and baseline, as we do not wish to impede any active quit attempt. We will assess desire to quit smoking at screening and each laboratory visit, and any indication of a desire to quit will result in ineligibility from the laboratory phase of the study if a participant chooses not to continue using the study cigarettes. Participants who choose not to use the study cigarettes will be allowed to remain in the study and complete the remaining study assessments if they desire. Individuals will be provided tobacco cessation resources upon request or at the end of the study (if not provided earlier). We will exclude participants who indicate suicidal ideation

as the potential to undergo nicotine withdrawal may exacerbate symptoms of depression. All female participants will be tested for pregnancy at each smoking visit or session. If a participant becomes pregnant during the study, she will be withdrawn from the study. Individuals will be provided referrals for treatment, where needed or desired, and at the 30-day follow-up. Males and females of any ethnic or racial group are eligible to participate in the study if they meet inclusion/exclusion criteria.

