Compensatory smoking and/or other tobacco use. The risk of compensatory smoking or increased use of tobacco products will be minimized by tracking daily cigarette and alternative tobacco product consumption assessed via EMA; and evidence of CO increase beyond acceptable levels (assessed at each in-person visit) will result in withdrawal from the study (see DSMP for further details). To minimize the risk of compensatory smoking or increased use of tobacco products, participants' daily smoking will be monitored for any increase as described in detail in the DSMP, and participants will be withdrawn if a marked increase in smoking or other tobacco use is evident. We note that in a recent trial of VLNC cigarettes in which adult smokers were given access to SPECTRUM cigarettes including VLNC doses for 6 weeks and expected to smoke only those cigarettes, there was no evidence of compensatory smoking, neither as measured by cigarettes per day nor by cotinine or toxicant exposure; therefore, we do not expect compensation to occur. Similarly, as noted above, in Co-I [name]'s current field trial of these cigarette doses in adolescents, we have not yet seen significant compensation (N=45 complete as of 2/2018); therefore, this outcome is unlikely. However, we will monitor indicators of increased smoking and alternative tobacco as discussed below and in the DSMP. We will work closely with our consultants to determine decision rules regarding removal from the trial and/or resumption of usual brand cigarettes based on the number of daily reported cigarettes and weekly CO levels to ensure that participants' risk is not increased.

Smoking in the laboratory. Smoking a single cigarette in the lab is used to measure potential compensatory smoking, an important issue under study. Risks related to cigarette puffing will be minimized by limiting this procedure to only one cigarette to and individuals who are smoking "somedays" or "everyday" for > the past 3-months who have no desire to quit. The laboratory where sessions will be completed was constructed with a special ventilation system for quickly removing smoke from the experimental rooms to reduce excess smoke exposure to participants and researchers.

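### Section B describes recruits who began regular smoking under 6 months ago and draws inference to new smokers, but eligibility sets a 3-month minimum and no maximum

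*Combined protocol and SAP*

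**What the plan says.** **Population as described.** The study-overview paragraph of Section B, which introduces the Dual-Reinforcement Model, says "We will recruit 172 menthol smoking YAs and adults aged 26-34 who started smoking regularly". After a parenthesis defining regular as some days or every day, the sentence continues "< 6-months ago, and assess appeal/reinforcement to smoking SPECTRUM menthol and non-menthol VLNCs". The Abstract says the sample is meant to catch smokers near the start of their smoking history. In Section B, the paragraph on gaps in the literature puts the open question in terms of inexperienced menthol smokers, and the abuse-liability paragraph notes that most earlier trials left out young adult new smokers. The policy paragraph just before the Conceptual Framework places its inference "in YAs and adults aged 26-34 who are new to smoking".

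**Population as enrolled.** F.1.a admits ages 18 to 34. F.1.b asks for someday or everyday smoking "for at least the past 3-months". The narrative after the exclusion list repeats the floor: "smokers for at least the last 3 months, thus the laboratory and take home smoking will confer no additional risks beyond their usual smoking". Section I.2, on smoking in the laboratory, repeats it again with a greater-than sign before "the past 3-months who have no desire to quit". The exclusion list ends with item f, "Strong preference for non-menthol cigarettes (smoke non-menthol > 80% of the time". Nothing in it concerns how long a person has smoked.

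**Analysis.** J.2 (Aim 1) lists age of smoking onset as a potential covariate. J.5 plans exploratory comparisons by age band (18-24 versus 25-34), sex, race/ethnicity and alternative product use. Duration of smoking is not named as a moderator.

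**The concern.** Two populations are described. One is people in their first half-year of regular smoking, and the Background's claim to add something new leans on them: it contrasts them with the established smokers in whom reduced-nicotine cigarettes have mostly been studied. The other is current menthol smokers in a 16-year age band with no limit on smoking history, and that is the group the criteria admit.

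What is at stake is the scope of the conclusion. The results are intended to inform a regulator on menthol under a nicotine standard, including effects on uptake. If the sample is largely long-term smokers, an average menthol versus non-menthol difference in it cannot simply be presented as the response of people new to smoking. The response may or may not differ by duration, and the plan as written would not show which.

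**Working it through.** No stated figure has to be reproduced. The check compares every statement of smoking duration.

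| Place | Minimum | Maximum |
|---|---|---|
| Section B, study overview | none | under 6 months since starting regular smoking |
| Section B, policy paragraph | none | none in figures; described as new to smoking |
| F.1.b | 3 months | none |
| Section F narrative | 3 months | none |
| I.2, smoking in the laboratory | more than 3 months | none |
| F.1 items a-e and F.2 items a-f, all read | 3 months (F.1.b) | none |

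**Step 1: can the statements be combined?** Taken together they would give a window of at least 3 and under 6 months. The ceiling, however, appears only in the Background and in none of the three places where eligibility is stated. The Baseline Session (V1) text has staff judge eligibility against the inclusion and exclusion criteria. A ceiling that is not among those criteria is not applied.

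**Step 2: what does Section F admit?** Take a 34-year-old who began at 18 (an illustrative case, not from the documents): 34 − 18 = 16 years. That person meets the duration criterion and would fall outside the Background's description. An earlier start would give a longer history.

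**Step 3: what share of the sample is recent starters?** The documents give no figure. Section F is compatible with any share from none to all, so no number for new smokers can be derived.

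**Step 4: does the analysis repair it?**
- Age of onset is only a potential covariate, and only in Aim 1.
- A person-level main effect adjusts the level of the response. It does not show whether the within-person cigarette contrast varies with smoking history; that needs an interaction.
- Onset age without current age is not duration, and current age is not in the Aim 1 covariate list.
- The EMA and ETM analyses (J.3, J.4) name neither onset nor duration.
- Age band is a poor stand-in: a 30-year-old may be a recent starter and a 22-year-old a long-term smoker.

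**Step 5: are the data there?** The Measures Descriptions list age at first use, and J.2 names an undefined age of smoking onset. Neither is shown to be the start of regular someday or everyday smoking, which is the event the Background counts from.

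**The case against.** The best defence is that this is Background wording. The policy paragraph is conditional, the Specific Aims and hypotheses do not mention new smokers, J.1 defines the sample simply as menthol smokers aged 18-34, and no planned analysis estimates an effect in recent starters. The Abstract can be read as using age as a proxy for an early smoking stage, and the 26-34 group is justified by its high menthol use. Potential adjustment for onset age, dependence and cigarettes per day, with the exploratory age comparison, covers related variation. All of this stands, and it limits the point to the described population and the reach of the conclusions. It does not remove the conflict, because the recruitment sentence is a flat statement about all 172 participants.

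Three stronger readings are tempting and are not supported.

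- *The main comparison is invalid.* It is not. Each participant smokes both research cigarettes, so the contrast is sound for whoever Section F admits, and the sample-size reasoning does not depend on duration.
- *The protocol's own theory says conditioning drives the effect, so longer smoking means a larger one.* The Conceptual Framework offers two explanations for menthol's pull at low nicotine: that it is pleasant in itself, or that it has become rewarding through pairing with nicotine. It never says that the effect grows with years smoked.
- *A detectable effect for new smokers can be quoted.* That needs their share of the sample, which the documents do not give. A subgroup figure would also not describe the precision of an interaction.

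**Conclusion.** The point holds as a mismatch between the stated and the enrolled population. Section B describes under 6 months of regular smoking; Section F admits 3 months upward without limit, about 16 years in the example. Conclusions should be about menthol smokers aged 18-34 as Section F defines them. Inference to people new to smoking is not supported by the main analysis alone.

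This rests on the text and on no statistical assumption. It does presume that recruitment follows Section F as written. How far the enrolled sample departs from new smokers cannot be sized from the documents. The matter should be corrected before results are written up.

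**What to change.** 1. **Reconcile the text.** Bring the Abstract and four paragraphs of Section B (literature gaps, abuse liability, study overview, policy inference) into line with Section F. Changing only the overview and policy paragraphs would leave the others inconsistent.
2. **For a trial already recruiting, change the description.** The Compensation section's reference to loss to follow-up above expectation suggests that this is the case. Remove the 6-month limit and the new-smoker wording, and state the population and conclusions as Section F defines them. Adding a ceiling to F.1.b instead would leave a 3-to-under-6-month window, would reach only later enrolments, and would carry a recruitment cost that the documents do not allow to be estimated.
3. **Confirm what is recorded.** Check whether age at start of regular smoking is collected, as distinct from age at first use.
4. **If it is, pre-specify one exploratory moderator.** Use years of regular smoking (current age minus age at start of regular smoking) by cigarette type, with both main effects. Limit any statement about newer smokers to that result and report its interval. Precision will be low: J.1 does not size the study for an interaction, and ages in whole years, if that is how they are recorded, cannot resolve 6 months.
5. **If it is not recorded**, make no statement about newer smokers.

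The cost is a narrower claim, a check of the data dictionary and one extra model term. Visits and the main comparison are unchanged.
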